Simonazzi et. al. analysed 2345 caesarean deliveries. Compared with patients who did not receive TXA, the study group had significantly less blood loss, (-160.27; 95% CI, -224.63 to-95.92), a lower drop in haemoglobin (-0.61 g/dL; 95% CI, -1.04 to -0.18), and a lower incidence of PPH and severe PPH. They also had less need for additional uterotonics (4.2% vs 7.3%; RR, 0.54; 95% CI, 0.36–0.81). The percentage of patients requiring blood transfusion during or after caesarean delivery was significantly lower in the TXA group (1.9% vs 5.7%; RR,0.33; 95% CI, 0.19–0.58). The adverse outcomes showed no significant difference: 2 patients in the intervention group and 2 in the placebo group experienced thromboembolic events (Table 1). This study was unique in that it had broader inclusion criteria, including multiple gestation pregnancies, as well as both labouring and planned caesarean deliveries. However, clinical heterogeneity

may have conflicted the results due to differences in TXA dosing, timing of intervention, and methods for measuring blood loss among the included studies (18).

A widely referenced study by Wang et al is a large meta-analysis of 11 RCTs where TXA was administered before the start of scheduled caesarean deliveries. This study also showed that TXA intervention significantly reduced intraoperative blood loss during and after caesarean delivery without an increase in thromboembolic events; this reduction was similar for both 1 g dosing and weight-based TXA dosing regimens. Similar to the meta-analysis by Simonazzi et al, prophylactic TXA was associated with a lower incidence of PPH, a smaller drop in postpartum haemoglobin, and a reduced requirement for blood transfusion (6).

A third large meta-analysis of prophylactic TXA use at the time of caesarean delivery, published as a Cochrane Review, produced similar outcomes to other large meta-analyses. For scheduled elective caesarean deliveries, TXA use was effective in reducing the incidence of PPH and blood transfusion requirements. As in other studies, gastrointestinal adverse effects, such as nausea and vomiting, were the most common adverse outcomes. Of note, the authors concluded that the studies were too small and underpowered to detect the effect of TXA on risk of maternal death or thromboembolism (17).

Similar outcomes are described among small RCTs of TXA use before caesarean delivery (19–23).

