 - o mean peripartum change in haemoglobin and haematocrit as well as haemoglobin drop > 2 g/dL,
 - o transfer to intensive care unit (ICU),
 - o or death from any cause.
- To assess potential adverse effects of TXA:
 - o Hemodynamic parameters,
 - o adverse gastrointestinal events, renal, hepatic, and coagulation function,
 - o and any venous or arterial thrombosis at any time during the woman's postoperative course.

METHODOLOGY

Research design

Open-label parallel randomized control trial.

Target population

Women undergoing caesarean sections at Sally Mugabe and Parirenyatwa Hospitals based on set inclusion and exclusion criteria.

Inclusion criteria

- Estimated gestational age of 37 weeks or more
- Live intrauterine foetus
- Elective or emergency caesarean delivery
- Signed informed consent

Exclusion criteria including any of the following factors or conditions identified prior to surgery

- History of coagulopathies or conditions predisposing them to thromboembolic phenomena,
- seizure history,
- autoimmune disease,
- placental abruption,
- placenta praevia,
- abnormally adherent placentae if identified on prenatal ultrasound,
- eclampsia or HELLP syndrome,
- known hypersensitivity to TXA,
- planned general anaesthesia,
- caesarean delivery for the second twin or second/third triplet(s) after vaginal birth of the first twin,
- poor understanding of English/Shona languages,
- those who have received anticoagulants in the week before delivery
- persons-under-investigation for COVID-19 and confirmed COVID-19 positive women.

Women will receive individual information in late pregnancy about the trial from obstetricians and midwives during antenatal clinic visits or from anaesthetists during the pre-caesarean visit, or both. Women may be pre-included (receive information and sign consent forms) for caesareans both before and during labour when the investigator considers that the woman is likely to have a caesarean delivery. The aim of pre-inclusion is to facilitate recruitment, particularly the recruitment of caesareans during labour, which may be decided upon and performed in emergency situations. Women recruited prior to emergency caesarean delivery (in labour) sign consent to have the caesarean section while in labour. We therefore consider that having received information about the trial during the antenatal period and on the labour ward, they will also be able to provide informed consent for inclusion into the trial at the same time.

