TXA obtained for the study will be kept in theatre. This is to ensure an uninterrupted supply of the drug for the study. The TXA vials will be kept in theatre in a locked drug cupboard accessible to the researcher and research assistants at the authorization of the sister in charge. A dispensing register for the drugs will be kept together with the drugs. Patient details and study number, amount of TXA dispensed and wasted will be entered into the study register for accountability and to guard against abuse.

Intervention

The participants in the intervention arm will receive generally from the anaesthetist or nurse anaesthetist TXA (1g), administered slowly (over 30 – 60seconds) at the time of skin incision. Participants in both the intervention arm and control group will receive the routine prophylactic 10 IU oxytocin intravenously at birth of the baby. All other aspects of management of the caesarean section will be identical in both arms (34).

Other aspects of the caesarean delivery

- The surgical team will decide on the administration of additional uterotonics and the management of PPH, in a manner consistent with local guidelines. In particular, the use of TXA for the treatment of PPH will be allowed and left to the practitioner's discretion according to the hospital protocol.
- Because the surgeon's level of experience may affect estimated blood loss during or after a caesarean delivery, the obstetrician's experience, categorized as senior resident medical officer, senior house officer, junior registrar, senior registrar or consultant will be recorded (34).

Assessment

Data will be collected and recorded on the data collection tool. Any adverse event will to be reported on the IRB adverse event reporting form.

Primary outcome measure

Estimated blood loss (EBL) will be determined using haematocrit, haemoglobin, and visual estimates.

Calculated estimated blood loss = estimated blood volume \times (preoperative haematocrit – postoperative haematocrit) / preoperative haematocrit. Where estimated blood volume (mL) = weight (kg) \times 85).

The calculation is an objective measure to estimate blood loss because of the inaccuracy of other methods used to determine blood loss and caesarean delivery(35).

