Preoperative haematocrit will be determined on the day before elective caesarean or on the day of emergency caesarean delivery. Postoperative haematocrit will be the haematocrit obtained by blood sampling at D2 (on the second morning after caesarean section). If haematocrit is not available at D2, then haematocrit at D3 will be considered; if it is also missing, then the postpartum haematocrit closest to D2 in the absence of transfusion will be considered (36,37).

All women who receive RBC transfusion for PPH between delivery and D2 postpartum are defined to have PPH and meet the criteria for the primary outcome. Calculated blood loss is impossible to determine for these women. Moreover, women only rarely receive an RBC transfusion for a blood loss less than 1000 ml. As a marker of significant maternal morbidity, RBC transfusion is considered equivalent or superior to blood loss greater than 1000 mL(25).

Although visual estimation is the method used frequently by anaesthetists to estimate blood loss, it has been demonstrated as inaccurate in repeated studies. The estimate of blood loss is affected by amniotic fluid as well. Its continued use in clinical practice is likely related to tradition and it being easily used. We will also take note of the visual estimate made by the anaesthetist, and by the operating surgeon, as this is the method used locally(6,38)(39)

Secondary outcome measures

Describing postpartum blood loss

1. Clinical

- a. Visually estimated blood loss
- b. proportion of women requiring supplementary uterotonic treatment
- c. incidence of postpartum transfusion
- d. mean number of RBC units transfused
- e. incidence of emergency surgery for PPH including caesarean hysterectomies
- f. incidence of hypovolemic shock related to PPH as determined by assessing BP and pulse
- g. incidence of transfer to ICU
- h. incidence of maternal death from any cause
- i. length of hospital stay.

2. Laboratory

- a. incidence of calculated blood loss > 500 mL and > 1500 mL
- b. mean total calculated blood loss
- c. mean peripartum change in haemoglobin (difference between haemoglobin before delivery and at D2)
- d. Haemoglobin drop > 2 g/dL (between haemoglobin before delivery and at D2) (34).

Describing adverse events

1. Clinical

a. Hemodynamic parameters (heart rate, blood pressure) 15, 30, 45, 60, and 120 min after delivery

- b. the occurrence of potential mild adverse effects of TXA in the operating room:
 - i. nausea
 - ii. vomiting

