 - iii. sensation of rings or spots of light in visual field
 - iv. dizziness
- c. the occurrence of potential severe adverse effects of TXA during the hospital stay and up to discharge
 - i. deep vein thrombosis, if the diagnosis is confirmed by Doppler ultrasound
 - ii. pulmonary embolism, if the diagnosis is confirmed by radiological examination
 - iii. myocardial infarction
 - iv. seizure
 - v. renal failure requiring dialysis
- d. any other unexpected adverse events

Data Management

The researcher and assistants will allocate each patient codes. No identifiers will be used. Any data collected will be stored in an office accessible only to the researcher and research assistants, as well as on a password-protected laptop computer.

data cleaning and entry

Completed questionnaires will be checked for validity, accuracy and completeness by the principal investigator before data entry into the computer.

Statistical methods and data reporting

Data analysis and reporting will be guided by the Consolidated Standards of Reporting Trials (CONSORT) and will be done by the researchers with the assistance of the statistician. (34).

The women's demographic characteristics and standard risk factors for PPH will be compared between the two groups.

The main analysis of the primary and secondary outcomes will be performed in the modified intention-to-treat (ITT) population, defined as women who undergo randomization and have a caesarean delivery (except if they withdraw consent or are deemed ineligible after randomization).

We will also analyse two separate per-protocol populations: women from the modified ITT population receiving a uterotonic and TXA (as specified in the protocol) (per-protocol group 1); the other will include women from the modified ITT population receiving a uterotonic and then tranexamic acid or no TXA in the 10min after delivery (per-protocol group 2; for a situation more consistent with routine clinical practice). The baseline characteristics of the trial participants, the management of the third stage of labour, and protocol adherence will be compared by descriptive statistics.

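### Nausea, vomiting, visual symptoms and dizziness count only while the woman is in theatre, a window with no clock time that conflicts with the plan's other outcome list

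*Combined protocol and SAP*

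**What the plan says.** Under Secondary outcome measures, Describing adverse events, the clinical list sets three different observation windows:

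- Haemodynamics have fixed times: "Hemodynamic parameters (heart rate, blood pressure) 15, 30, 45, 60, and 120 min after delivery".
- The four mild effects (nausea, vomiting, rings or spots of light in the visual field, dizziness) are tied to a place: "the occurrence of potential mild adverse effects of TXA in the operating room". No start, end or schedule for asking is given.
- Severe effects have a long window: "the occurrence of potential severe adverse effects of TXA during the hospital stay and up to discharge".

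The Secondary Outcomes list, earlier in the protocol, names "adverse gastrointestinal events, renal, hepatic, and coagulation function" with no limit of place or time.

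Two other routes exist for adverse events. The Assessment section states: "Any adverse event will to be reported on the IRB adverse event reporting form". The clinical list closes with "any other unexpected adverse events".

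TXA is "administered slowly (over 30 – 60seconds) at the time of skin incision". The statistical methods section reports binary outcomes as relative risks and absolute risk differences, with no adjustment for time observed.

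**The concern.** Adverse effects are the second of the trial's two objectives. The Literature review, describing a Cochrane review of prophylactic TXA, says that "gastrointestinal adverse effects, such as nausea and vomiting, were the most common adverse outcomes". Nausea and vomiting are therefore among the safety outcomes that a trial of this size can estimate best. That statement does not cover visual symptoms or dizziness.

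A window defined by a room has two weaknesses. It closes when the woman leaves, so a symptom that starts soon afterwards does not count. Its length also differs between women, for reasons that the plan neither records nor controls.

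The two outcome lists also disagree on whether vomiting in recovery is an outcome event. An analyst could settle that either way after seeing the data.

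**Working it through.** **1. The plan's own figure.** The documents give no side-effect rate, theatre time or sample size for this outcome. The only relevant design figure is the sample size. The stated formula with 2.1% vs 5.8%, two-sided 5% and 90% power gives 581 per group with unrounded normal quantiles (579.8 with the printed 1.96 and 1.28). The plan's 581 is reproduced and used below.

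**2. Do the other routes bring later events into the outcome?** The ethics-board form takes any adverse event, but nothing says that its reports feed this outcome. The closing item covers unexpected events, and nausea and vomiting are listed as expected. Vomiting 90 min after delivery, out of theatre, might be reported but would not count in the defined mild-effect outcome.

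**3. Cost of missed events.** Let *s* be the share of events that start after theatre, equal in both arms. This share is an assumption; the documents give nothing from which to estimate it.

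- Relative risk: unchanged, because both rates are multiplied by (1 − *s*).
- Absolute rates and risk difference: multiplied by (1 − *s*).
- Width of the log-scale confidence interval: multiplied by about 1/√(1 − *s*). For *s* = 0.20, 1/√0.80 = 1.118, about 12% wider. For *s* = 0.50, 1/√0.50 = 1.414, about 41% wider.

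This is the rare-event form. With the full standard error √(1/a + 1/b − 2/581), where a and b are the event counts, and assumed true rates of 15% vs 10%, the values are 0.159 for all events, 0.180 at *s* = 0.20 and 0.232 at *s* = 0.50. That is 13% and 46% wider, so 12–41% is slightly on the low side for common symptoms.

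Power for the same assumed rates at 581 per arm:

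| Share missed | Risk difference (points) | Power |
|---|---|---|
| 0 | 5.0 | 73% |
| 25% | 3.75 | 59% |
| 50% | 2.5 | 42% |

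**4. Unequal observation time.** Suppose that every woman has a base stay and only PPH cases stay longer. Mean stay = base + extra × PPH rate. The PPH rates come from the documents: the design rates (2.1% TXA, 5.8% control) and the pilot per-protocol rates (22.6%, 31.4%). Base and extra minutes are assumptions.

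- With 15–60 extra minutes per case, the control mean is longer by extra × rate difference. At the design rates this is 15 × 0.037 = 0.6 to 60 × 0.037 = 2.2 min. At the pilot rates it is 15 × 0.088 = 1.3 to 60 × 0.088 = 5.3 min.
- Take a 60-min base, no true TXA effect and a constant hazard of 15% per 60 min. The risk over 60 + *e* minutes is 1 − 0.85^((60+*e*)/60): 0.184 for *e* = 15 and 0.2775 for *e* = 60.
- Design rates, *e* = 60: TXA 0.979 × 0.15 + 0.021 × 0.2775 = 0.1527; control 0.942 × 0.15 + 0.058 × 0.2775 = 0.1574; ratio 0.97. With *e* = 15 the ratio is 0.99.
- Pilot rates, *e* = 60: 0.1788/0.1900 = 0.94. With *e* = 15 the ratio is 0.98.

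The null relative risk therefore moves to 0.94–0.99.

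**5. What would a large time bias need?** For the TXA mean stay to be a fraction *r* of the control mean, with a 60-min base, the extra minutes per PPH case must be 60(1 − *r*)/(*r* × control rate − TXA rate).

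| *r* | Design rates | Pilot rates |
|---|---|---|
| 0.90 | 6/0.0312 = 192 min | 6/0.0566 = 106 min |
| 0.80 | 12/0.0254 = 472 min | 12/0.0252 = 476 min |

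Stays prolonged by that much in every PPH case are not a reasonable basis for a bias claim.

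**The case against.** The strongest defence is that a theatre window is a defensible choice. TXA is given at skin incision, so the window covers the period straight after the randomised dose. Additional uterotonics and treatment TXA are allowed at the team's discretion, so later symptoms may have other causes. The outcome is secondary, no power is claimed for it, and an equal loss in both arms leaves the relative risk unbiased. Later events may still reach the ethics-board form, and the data collection tool, which is not in the text available, may set times for asking.

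Much of this stands. It rules out three stronger readings that a reader might infer:

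- *TXA, by reducing bleeding, will markedly lower its own side-effect count.* No section gives theatre times, links them to bleeding or says that TXA shortens surgery. On the documents' PPH rates the effect is small.
- *Later events are lost altogether.* They may be reported; what the text shows is that they are outside the defined outcome.
- *All four symptoms are the commonest side effects.* The cited review supports this for nausea and vomiting only.

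The defence does not settle the conflict between the two outcome lists, and it gives no reason for ending the window at a doorway rather than a time. Symptoms that follow rescue treatment do not undermine the comparison of arms as randomised, although they do affect how the rates are read.

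**Conclusion.** The point holds as a problem of outcome definition. The mild-effect outcome is bounded by location, has no clock time, varies between women, and disagrees with the unrestricted gastrointestinal item in the Secondary Outcomes list. Rates over the early postoperative period will be understated and precision lost if any symptoms start after theatre. The amount cannot be derived from the documents; 12–41% wider intervals correspond to an assumed 20–50% of events missed, equally in both arms.

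Unequal observation time is a minor addition. It is conditional on bleeding prolonging theatre stay and is worth a null relative risk of about 0.94–0.99 under assumed base and extra stays and a constant hazard. The primary outcome is not affected. The change is worth making because it is cheap and serves a stated objective.

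**What to change.** Reconcile the Secondary Outcomes list with Describing adverse events by stating one definition: any nausea, vomiting, visual symptom or dizziness from skin incision to 120 min after delivery, in both arms.

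- Record events in theatre as they occur. The first scheduled reading is 15 min after delivery, so the period just after dosing would otherwise rest on recall.
- Ask the same yes/no questions in the same words at the scheduled 15, 30, 45, 60 and 120 min readings, wherever the woman is.
- Analyse any event in that window by arm, and keep the operating-room count as a supporting analysis close to the dose.
- State whether reports on the ethics-board form feed this outcome.

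The window is not strictly equal in length, because time from incision to delivery varies. Its end is set by the clock, however, and no longer by when the woman leaves theatre.

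The cost is slightly more bedside recording at contacts already planned; the plan does not say who takes these readings or on what form, so that needs confirming. Later symptoms may partly reflect additional uterotonics or treatment TXA. The trial stays open-label, so standard questions reduce uneven asking but do not remove knowledge of the arm.

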PPH contributes to near-miss cases in addition to actual deaths, due to the serious complications that can occur as a consequence of serious PPH. These include adult respiratory distress syndrome, coagulopathy, shock, loss of fertility, and pituitary necrosis (Sheehan syndrome) (4). If PPH is prevented this could contribute towards reduced hospital stay, avoidance of expensive interventions for intractable PPH (such as hysterectomies and the need for blood products) and conserve our already strained resources.

Prophylactic TXA use has been shown to produce a statistically significant decrease in postpartum blood loss; however, this may not convey clinical significance in terms of transfusion rates and maternal comorbidity from severe haemorrhage. Currently, there is no consensus regarding the optimal timing or dosing of prophylactic TXA for caesarean deliveries (33).

In the light of the above, this research proposes to assess the efficacy of TXA in preventing PPH after caesarean delivery in a population large enough to be adequately powered to add to the current body of evidence. Also, there are no published RCTs, in Southern Africa reporting on TXA in obstetric patients.

GOAL STATEMENT

The aim of this study is to compare the effect of a low dose of TXA (1 g) at the time of skin incision during caesarean delivery together with prophylactic oxytocin administration, versus prophylactic oxytocin alone in an open label randomized clinical trial.

RESEARCH QUESTION

Does intravenous TXA 1g plus Oxytocin 10 IU result in a lower incidence of primary postpartum haemorrhage compared to Oxytocin 10 IU alone after caesarean section?

OBJECTIVES

- 1. To assess the effect of TXA (1g) on postpartum blood loss at caesarean delivery.
- 2. To determine the potential adverse effects of intravenous TXA administered at caesarean section.

PRIMARY OUTCOME

Incidence of PPH, defined by a calculated estimated blood loss > 1000ml or a red blood cell transfusion up to day 2 postpartum

Secondary Outcomes

- Other outcome measures describing postpartum blood loss including
 - o calculated blood loss,
 - visually estimated blood loss,
 - o mean/median number of units of packed red blood cells transfused,
 - o incidence of postpartum shock;
 - o proportion of women requiring supplementary uterotonics,
 - o incidence of postpartum transfusion,
 - o incidence of emergency surgery for PPH including caesarean hysterectomies,

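### The main analysis set excludes women judged ineligible after randomisation in an open-label trial, with no time limit or masking on that judgement and no planned analysis that puts them back

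*Combined protocol and SAP*

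**What the plan says.** Under Statistical methods and data reporting, "The main analysis of the primary and secondary outcomes will be performed in the modified intention-to-treat (ITT) population". That population is defined as "women who undergo randomization and have a caesarean delivery (except if they withdraw consent or are deemed ineligible after randomization". The section does not say who makes the ineligibility judgement, by when, on what information, or whether that person is unaware of arm and outcome.

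The other planned populations are nested inside this one: "We will also analyse two separate per-protocol populations: women from the modified ITT population receiving a uterotonic and TXA", with the second per-protocol set also taken from the modified ITT population. No analysis of all randomised women is planned.

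Four other places bear on the point:
- Research design: "Open-label parallel randomized control trial".
- The exclusion list opens with "Exclusion criteria including any of the following factors or conditions identified prior to surgery".
- Data cleaning and entry: "Completed questionnaires will be checked for validity, accuracy and completeness by the principal investigator before data entry into the computer". Masking to arm or outcome is not mentioned.
- Primary outcome: "Incidence of PPH, defined by a calculated estimated blood loss > 1000ml or a red blood cell transfusion up to day 2 postpartum".

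**The concern.** Randomisation protects the comparison only while membership of the analysis set does not depend on arm and outcome together. Here the arm is known to everyone, heavy bleeding and transfusion are visible to the clinical team, and a woman can still leave the main analysis after both are known.

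Several listed exclusions are themselves bleeding-related: history of coagulopathy, abruption, praevia, and abnormally adherent placenta seen on prenatal ultrasound. A woman who bleeds heavily is more likely to have her record searched for one of these than a woman who does not. If the search, or the decision to act on what it finds, differs between arms, events are lost unequally. Because every planned analysis starts from the reduced set, the report would contain no result against which to check this.

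At stake is the primary risk ratio. The design expects few events, so the result is sensitive to a small number of selective removals.

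**Working it through.** **Inputs.** From Sample size: 2.1% PPH with TXA, 5.8% with control, two-sided 5% level (z = 1.96), 90% power, 1:1 allocation, 581 per group. From the literature review: 31.4% PPH among pilot women who did not receive TXA. The documents give no rate of post-randomisation exclusion, so every removal count below is an assumption.

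**The plan's own figure.** With mean proportion 0.0395:

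n = [1.96√(2 × 0.0395 × 0.9605) + z_β√(0.021 × 0.979 + 0.058 × 0.942)]² / 0.037²

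This gives 579.8 with z_β = 1.28 and 580.3 with z_β = 1.2816. The latter rounds up to the stated 581.

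**Expected events.** 581 × 0.021 = 12.2 and 581 × 0.058 = 33.7, so about 12 against 34, or 46 in all.

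**Extreme scenario.** Assume no true effect, the same PPH rate in both arms, and k women removed from the TXA arm, all of them PPH cases. With 34 events per arm:

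RR = [(34 − k)/(581 − k)] / (34/581)

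For k = 12: (22/569)/(34/581) = 0.03866/0.05852 = 0.66.

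The false-positive rate is the probability, over two independent binomial counts with n = 581, that after removal

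z = (p_T − p_C)/√[p(1 − p)(1/n_T + 1/n_C)] < −1.96, with p the pooled proportion.

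| TXA-arm cases removed | Share of arm | Share of its 34 events | RR at 5.8% | False positive for TXA, 5.8% PPH | Same, 31.4% PPH |
|---|---|---|---|---|---|
| 0 | 0% | 0% | 1.00 | 2.5% | 2.5% |
| 3 | 0.5% | 9% | 0.92 | 5.9% | 3.4% |
| 6 | 1.0% | 18% | 0.83 | 12.5% | 4.6% |
| 9 | 1.5% | 26% | 0.75 | 23.0% | 6.1% |
| 12 | 2.1% | 35% | 0.66 | 36.5% | 7.9% |

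**Milder scenarios at 5.8%.**
- Six removed from the TXA arm only, half of them cases: about 6%.
- Twelve removed from the TXA arm only, half of them cases: about 12%.
- Twelve cases removed from each arm: RR stays at 1.00 and the rate is just under 6%.

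**Single-trial illustrations.** With 34 events in each arm, 15 TXA cases (44% of that arm's events) must go before the result is significant: 19/566 against 34/581, RR 0.57 (95% CI 0.33 to 0.99), p = 0.044. A borderline result is more fragile: 20/581 against 34/581 gives p = 0.051, and removing one TXA case (19/580) gives p = 0.035.

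**The case against.** The strongest defence is the wording of the exclusion list. It covers conditions identified before surgery, adherent placenta counts only when prenatal ultrasound showed it, and coagulopathy counts only as history. The ineligibility clause most naturally refers back to that list. A reader might infer that an abruption or adherent placenta discovered at operation could be used to remove a woman who then bled. The documents do not support that: such a condition is not an exclusion criterion. This part of the defence stands. It does not cover a criterion that was present and on record beforehand but noticed only when bleeding prompted someone to look.

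A reader might also object that the population omits randomised women who have no caesarean. That is not a fault worth pressing. TXA is given at skin incision, so randomisation must come first. The passage allowing early inclusion ("Women may be pre-included (receive information and sign consent forms) for caesareans both before and during labour") concerns information and consent, not randomisation. The fix below keeps the same restriction.

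Third, calculated blood loss rests on a day-2 haematocrit, so someone judging in theatre does not know the primary outcome and would remove a mixture of cases and non-cases. This is fair, and it is why the half-case scenarios are shown. It does not help with a judgement made after day 2, and transfusion, which also counts as PPH, is visible as it happens. An objective measurement protects how the outcome is measured, not who is counted.

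Finally, the larger figures need a low event rate, wholly one-sided removal, and every removed woman to be a case. That also stands, and it limits what can be claimed.

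**Conclusion.** The point holds in a limited form. The main analysis allows women to be removed after randomisation, in an open-label trial, through a judgement with no stated time limit or masking, and nothing planned shows the result without those removals. This is a route to bias that the text leaves open. It is not evidence that bias will occur.

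A reader might take 36.5% as the expected false-positive rate. The documents do not support that: they give no removal rate and no sign of one-sided removal. The figure assumes no true effect, 5.8% PPH, and 12 removals that are all TXA-arm cases, about a third of that arm's events. With half the removed women being cases, the rate is about 6% for 6 removals and 12% for 12. If PPH is as common as the 31.4% seen in the pilot, the extreme scenario reaches only about 8%.

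The pilot was significant per protocol but not by intention to treat. That shows the choice of analysis set can matter in this setting. It does not show that ineligibility removals caused the difference.

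The wording should be changed before outcome data are examined, because the change is cheap and cannot be made credibly afterwards.

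**What to change.** In Statistical methods and data reporting:

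1. Delete the part of the exception that covers ineligibility judged after randomisation. Define the main population as all randomised women who have a caesarean, analysed in their assigned arm, leaving out only those who withdraw consent to use of their data.
2. Keep the set without ineligible women as a sensitivity analysis. Limit it to criteria from the protocol's exclusion list that were documented before surgery.
3. Report the number of exclusions and the reason for each, by arm.

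The cost is a change of wording and one further analysis. The sample size is unchanged at 581 per group. The statistical downside is slight dilution of the effect from a few truly ineligible women, which the sensitivity analysis would show.
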